### **Intraocular Pressure.**

The Baseline intraocular pressure within an eye will be determined as the average of the Screening and Day 1 (also called Baseline in the protocol) pre-injection measurements. Non-integer values for the average will be rounded up prior to subsequent calculations of change from baseline.

IOP will be summarized by visit, including all pre-injection, “IOP after first injection” and “IOP after second injection” measurements. An additional tabular summary of the percentage of subjects in categories of IOP will be presented by cohort, visit, and injection time (pre-injection, IOP after first injection, IOP after second injection).

“IOP after first/second injection” is defined as the IOP measurement that is closest in time to the protocol-specified post-injection timepoint (but at least 25 minutes post-injection). If there are two closest measurements equidistant to this timepoint, then the measurement after the protocol-specified timepoint will be used.

Mean IOP over time of all scheduled measurements (pre-injection, IOP after first injection, and IOP after second injection) will be plotted.

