4.5.2 Study OPH2001

A separate phase 1 study was also performed in subjects diagnosed with geographic atrophy (GA). In this study, a total of 47 subjects were enrolled, in the 0.3 mg dose arm (n=24) and 1 mg dose arm (n=23). Subjects received treatment with 3 initial intravitreal injections of Zimura™ 0.3 mg/eye or 1 mg/eye, administered at Day 0, Week 4 and Week 8 with a follow up visit at Week 16. Subjects received 2 subsequent injections at Week 24 and Week 36 followed by a final follow up visit at Week 48. Standard safety assessments were performed for ophthalmic variables that included VA, IOP, ophthalmic examination, fundus autofluorescence (FAF), Fluorescein Angiography (FA), and optical coherence tomography (SD-OCT) together with AEs, vital signs and laboratory variables.

Zimura™ was well tolerated and there were no AEs considered to be related to Zimura™. Fifteen subjects (32%) had AEs, predominantly Eye Disorder AEs in the study eye, assessed to be related to the injection procedure. The most frequently reported AEs were conjunctival hemorrhage (4 subjects, 9%), corneal edema (4 subjects, 9%), and dry eye (3 subjects, 6%). No other study eye AEs were reported by more than 2 subjects. The majority of AEs were mild or moderate in severity. There were 2 subjects with AEs of severe intensity: gastrointestinal inflammation and nasopharyngitis.

Five subjects experienced serious adverse events (SAEs), namely device failure, pelvic fracture, angina pectoris, chest pain and gastrointestinal inflammation, but none were related to the study drugs or injection procedure. There were no discontinuations due to AEs.

Vital signs and laboratory assessments did not show any particular clinically significant patterns or changes. Study eye ophthalmic examinations did not indicate any unexpected clinical findings. There were some transient findings post-injection (conjunctiva/sclera and cornea) that resolved prior to the next injection. Vitreous haze was also reported for a few subjects. Intraocular pressure (IOP) showed a small mean increase following injections but no indication of any cumulative increases.

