### **3.3.4 Handling Missing or Partially Missing Dates**

Missing or partially missing dates will not be imputed at data level. However, assumptions for missing or partially missing dates for important variables will be made to allow inclusion of appropriate data records in the analyses. In general, the assumptions about the missing or partially missing dates, when needed, are made conservative to avoid overestimation of treatment effect and underestimation of adverse effects.

[figure not shown]
If a medication date or time is missing or partially missing, so it cannot be determined whether it was taken prior or concomitantly, it will be considered both as a prior and a concomitant medication.

If the partial AE onset date information does not indicate whether the AE started prior to treatment or after treatment, the AE will be classified as after treatment.

---

[Redacted text block containing several lines of text and a bulleted list item, all obscured by black bars.]

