### **5 DEMOGRAPHIC AND OTHER BASELINE CHARACTERISTICS**

Descriptive statistics will be provided to document baseline demographic information. This information may be used to informally assess similarity of the randomized groups at baseline, although no formal comparison will be conducted.

Descriptive statistics with respect to subject characteristics at baseline will be displayed for the Safety population. When several measurements are available before the first administration of study drug, the baseline value is the last available value prior to first dose, except for the baseline visual acuity score and baseline intraocular pressure which are the mean of the screening and Day 1 pre-injection values.

The variables to be summarized are:

- Gender, Ethnicity, Race, Iris color, Age, Current smoking status, Study Eye, Region
- Prior ocular history, both eyes (by MedDRA preferred term, including number and percentage of all Subjects with at least one prior ocular history)
- Medical history (excluding ocular history) (by body system and preferred term, with number and percentage for both; including number and percentage of all subjects with at least one prior medical history)
- Prior surgeries/procedures (by body system and preferred term, with number and percentage for both; including number and percentage of all Subjects with at least one prior surgery/procedure)
- Vital signs (Height, Weight, Pulse, Blood pressure, Respiratory Rate)
- ECOG performance status
- Visual acuity, both eyes
- Tonometry, both eyes
- ECG
- Ophthalmic exam, both eyes (Motility, Lids/Lacrimal/Lashes, Conjunctiva/Sclera, Cornea, Anterior chamber activity: cells, Iris, Pupils, Lens Status, Vitreous haze, Vitreous hemorrhage, Posterior vitreous detachment, Optic nerve, Macula, Retinal vessels, Peripheral retina)

- Imaging Assessments, study eye
  - Fluorescein Angiography:
    - CNV location (extrafoveal, juxtafoveal, subfoveal)
    - CNV type (predominantly classic, minimally classic, occult)
    - Area of choroidal neovascularization (CNV) (defined as classic CNV + occult CNV + RPE staining in mm^2)
    - Area of total lesion (mm^2)
  - Optical Coherence Tomography (OCT)
    - SHRM within the center 1mm (yes/no)
    - SHRM (μm)
    - RPE elevation
    - Central subfield thickness (μm)

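### SAP 7.7 rounds the Baseline IOP average up, so any IOP change from baseline is biased slightly low (about 0.25 mmHg on the mean) with no stated reason

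*SAP*

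**What the plan says.** SAP Section 7.7, under Intraocular Pressure, sets the Baseline: "The Baseline intraocular pressure within an eye will be determined as the average of the Screening and Day 1" pre-injection measurements. The next sentence is the rule at issue: "Non-integer values for the average will be rounded up prior to subsequent calculations of change from baseline". This governs calculation, not display.

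SAP Section 5 takes the last value before first dose as Baseline for most variables, "except for the baseline visual acuity score and baseline intraocular pressure which are the mean of the screening and Day 1 pre-injection values". It gives no rounding step.

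Section 7.7 then names three IOP outputs:
- a by-visit summary: "IOP will be summarized by visit, including all pre-injection" and post-injection values;
- a categorical table: "An additional tabular summary of the percentage of subjects in categories of IOP will be presented by cohort, visit, and injection time";
- a plot: "Mean IOP over time of all scheduled measurements".

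None is described as a change from baseline, although the rounding sentence expects such a calculation. By contrast, Sections 7.6 (vital signs) and 7.8 (laboratory) name their change-from-Baseline outputs explicitly. SAP Section 2.1.1 lists IOP among the safety endpoints, and safety is the trial's only objective.

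**The concern.** The average of two readings is raised whenever it is not a whole number and is never lowered. The follow-up value is a single reading and stays as recorded. The error in follow-up minus Baseline therefore has one sign, and averaging over more subjects does not remove it. For IOP the adverse direction is upward, so the rule shrinks rises and enlarges falls.

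The two sections also allow two Baselines for the same eye: the plain mean in the baseline table and the rounded value in a change calculation. A reader who subtracts the tabulated baseline mean from a tabulated visit mean would not recover the reported mean change, even with complete data.

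All four cohorts receive the study drug with ranibizumab and there is no ranibizumab-only arm. Within-cohort change from baseline is therefore a natural way to read IOP, and it is the quantity that is shifted.

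**Working it through.** The plan gives no figure for the effect of rounding, so there is nothing to reproduce. The size follows from the rule.

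**Inputs.** Two Baseline readings S (Screening) and D (Day 1), and the ceiling rule, all from SAP 7.7. The follow-up reading F is not rounded. Reading precision is not stated in the visible text and is an assumption below.

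**Shift per eye.** m = (S + D)/2; Baseline under 7.7 is B = ceil(m); shift = B − m, with 0 ≤ shift < 1 mmHg at any precision. Reported change = F − B = (F − m) − shift, so the change is lowered or left alone and never raised.

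**Whole-mmHg readings.** S + D is even (shift 0) or odd (shift 0.5). If p is the proportion of eyes with an odd sum, the bias in mean change is −0.5p.
- p = 0: 0 mmHg
- p = 0.5 (odd and even about equally common): −0.5 × 0.5 = −0.25 mmHg
- p = 1: −0.5 mmHg

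**Simulation check.** Nine scenarios of 1,000,000 eyes each were run (assumed mean IOP 14 to 16 mmHg, SD 3 to 4, correlation between the two readings 0.5 to 0.9). The proportion of non-integer averages was 0.499 to 0.501 and the mean shift 0.249 to 0.250 mmHg, with a maximum of 0.5.

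**Half-mmHg readings.** The average can end in .00, .25, .50 or .75, giving shifts of 0, 0.75, 0.50 and 0.25. If these are equally common, the mean shift is 1.50/4 = 0.375 mmHg (simulation 0.375) and the maximum 0.75.

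**Examples.** S = 15, D = 16, so m = 15.5 and B = 16.
- F = 18: unrounded change +2.5; under 7.7, +2.
- F = 13: unrounded change −2.5; under 7.7, −3.

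**Trend between post-baseline visits.** (F at Month 6 − B) − (F at Month 1 − B) = F at Month 6 − F at Month 1. B cancels within each subject.

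**Between cohorts.** Every cohort has the same expected shift. The realised average varies a little by chance: with p = 0.5 the per-eye SD of the shift is 0.25, so its standard error is 0.25/√10 = 0.08 mmHg for 10 subjects and 0.25/√20 = 0.06 mmHg for 20.

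**Thresholds on change, whole-mmHg readings.** For an odd sum, F − m = j + 0.5 and F − B = j, where j is an integer. Then j + 0.5 ≥ k exactly when j ≥ k, so a cut of k or more classifies every eye the same way. A strict cut above k differs when j = k. Enumeration over Baseline readings 5 to 30, follow-up 5 to 60 and k = 5, 10, 15, 20 agreed: 0 reclassified for k or more, 1,352 combinations for strictly above k. The only IOP threshold measured from Baseline in the documents is the dose-limiting toxicity criterion in Protocol 9.2.3.1 (a rise of 15 mmHg or more), which is of the unaffected kind.

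**The case against.** The strongest reply is that little depends on this sentence. No output named in 7.7 is a change from baseline. The by-visit summaries and the plot use recorded values, and the categories do too unless they are defined on change. Individual data are listed, and raised IOP is also captured as an ocular adverse event. All of that stands, and it keeps the point small. It does not rescue the rule: either change outputs are planned and will be biased, or the sentence has no use.

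Three stronger readings are tempting, and the documents do not support them.

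- A reader might infer that the rule masks a cumulative rise over a schedule of 12 to 18 study-eye injections. It cannot hide drift between post-baseline visits, because the offset is the same at each visit and cancels. Drift is also visible in the unrounded by-visit summaries and the plot.
- A reader might cite Protocol 4.5.2: "Intraocular pressure (IOP) showed a small mean increase following injections but no indication of any cumulative increases". That was a geographic atrophy study of Zimura without ranibizumab, and the increase described followed injections. It does not show that a shift of 0.25 mmHg would matter here.
- A reader might say that the rule breaks the SAP's own principle in Section 3.3.4, where assumptions are "made conservative to avoid overestimation of treatment effect and underestimation of adverse effects". That text concerns missing or partial dates. The contrast in direction is a fair analogy, not a breach.

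**Conclusion.** The point holds as a small, one-directional and avoidable bias in any derived IOP change from baseline, together with a mismatch between SAP 7.7 and Section 5. With whole-mmHg readings it is 0.5 mmHg for each affected eye. On the mean it is about 0.25 mmHg if odd and even values are about equally common, within a range of 0 to 0.5. Both the precision and the odd-even split are assumptions; at any precision the shift stays below 1 mmHg. The direction needs no assumption beyond unrounded follow-up values, and no visible text rounds them.

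It would go too far to say that the rule conceals harm. Absolute IOP results, trends between post-baseline visits and, with whole-mmHg readings, the dose-limiting toxicity cut are unaffected, and expected differences between cohorts are essentially unchanged. What remains is that rises from baseline are understated and falls overstated in a named safety endpoint, with no reason given.

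**What to change.** Delete the rounding sentence from SAP 7.7. Calculate change from the unrounded mean of the Screening and Day 1 pre-injection values, in line with Section 5, and round only when results are displayed (one decimal). In the same edit, state which IOP change-from-baseline outputs are planned, if any, and whether the IOP categories are defined on absolute values or on change. The cost is one sentence removed and one added. No new data are needed, trial conduct does not change, and there is no evident downside.

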3 STUDY ASSESSMENTS

Cohort 1

Assessment	Scr	Day 1 ¹ (Baseline)		Day 9 ⁷	Month 1		Month 2		Month 3		Month 4		Month 5		Month 6 /EW
		D0	D2		D0	D2	D0	D2	D0	D2	D0	D2			
Informed consent	X														
Medical & Ophthalmic history	X														
Vital signs/Physical exam ²	X			X											X
12-Lead ECG	X														X
Tonometry ^{3,4,5} / Ophthalmologic examination ⁵	X	X	X	X	X	X	X	X	X	X	X	X	X	X	X
Protocol refraction and VA using ETDRS chart ⁵	X	X	X	X	X	X	X	X	X	X	X	X	X	X	X
Color fundus photography ⁵	X	X ⁸							X						X
Fluorescein angiography ⁵	X	X ⁸							X						X
SD-optical coherence tomography (SD-OCT) ⁵	X	X ⁸		X	X		X		X		X		X		X
Laboratory tests	X			X											X
Serum pregnancy test (if applicable)	X														
Reconfirmation of Eligibility		X													
Zimura™ 4mg/eye: two Zimura™ 2 mg/eye Injections			X			X		X		X		X		X	
Lucentis® 0.5 mg/eye Injection		X			X		X		X		X		X		
3-Day Post-Injection Telephone Safety Check			X			X		X		X		X		X	
Concomitant medication assessment	X	X	X	X	X	X	X	X	X	X	X	X	X	X	X
Adverse events ⁶		X	X	X	X	X	X	X	X	X	X	X	X	X	X

¹Day 1 Visit assessments should be performed within 14 days of Screening.

²Physical examination is performed at Screening and at the Investigator's discretion thereafter. Vital Signs at all indicated timepoints.

³Goldmann applanation tonometry must be performed at Screening, Day 1, and Month 6/EW. The Tono-Pen may be used at other times; however, Goldmann applanation tonometry must be used to verify any IOP \geq 30mm Hg occurring more than 30 min post-injection, or any IOP \geq 30 mmHg at any other time.

⁴Tonometry should be measured prior to the first injection, after the first injection, and after the final injection and at any additional times as specified by the Intravitreal Administration Protocol (see Section 17.4).

⁵Ocular assessments performed at Screening, Month 3, Month 6, and Early Withdrawal should be performed on both eyes (OU). Ocular assessments at all other study visits are performed on the study eye (SE) only.

⁶All adverse events are to be recorded after first injection.

⁷Day 9 will apply to the DLT cohort only. The DLT cohort is defined as the first 3-6 subjects (depending on if DLTs are noted) enrolled in Cohort 1.

⁸Imaging at Day 1 may be repeated if required per section 10.2.1.1 Reconfirmation of Eligibility at Day 1

EW = Early Withdrawal Visit

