7.2 Tonometry

Tonometry will be performed at all time-points specified Sections 10.2 – 10.5 “Trial Assessments”. On days when two injections are given tonometry should be repeated after the first injection, to confirm perfusion of the optic nerve and return of IOP to ≤ 21 mmHg or within 5 mmHg of pre-injection before the second injection is administered. After the second injection, and also on days when only one injection is administered, IOP must return to < 30 mmHg before the subject leaves the clinic. For the post-injection tonometry, proper care should be taken to minimize the risk of contamination.

Goldmann applanation tonometry must be performed at Screening, Day 1, and Month 6/Early Withdrawal. Tono-Pen may be used at all other time-points, but Goldmann applanation tonometry must be used to verify IOP for a post-injection reading of ≥ 30 mmHg occurring more than 30 minutes post-injection, or for a reading of ≥ 30 mmHg at any other time.

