10.2.2 Day 1 (D0 Visit)

Pre-injection

- Protocol refraction and visual acuity (4 meters) using ETDRS chart (SE)
- Goldmann applanation tonometry and Ophthalmologic Examination (SE)

Injection

- Lucentis[®] 0.5 mg/eye

Post Injection

- Indirect Ophthalmoscopy (SE) – 1 to 2 minutes after the injection to assure that the optic nerve is perfused.
- Ophthalmologic exam/Tonometry (SE) – At least 30 minutes after the injection a full ophthalmologic exam must be performed and IOP must be < 30 mmHg before the subject leaves the clinic.

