10.2.3 Day 1 (D2 Visit)

Pre-injection

- Protocol refraction and visual acuity (4 meters) using ETDRS chart (SE)
- Tonometry and Ophthalmologic Examination (SE)

Injection

- Zimura™ 2 mg/eye – **dose 1**
 - Indirect Ophthalmoscopy (SE) – 1 to 2 minutes after the injection to assure that the optic nerve is perfused.
 - Ophthalmologic exam/Tonometry (SE) – After the injection, to confirm perfusion of the optic nerve and return of IOP to ≤ 21 mmHg or within 5 mmHg of pre-injection.
- Zimura™ 2 mg/eye – **dose 2**

Post 2nd Injection

- Indirect Ophthalmoscopy (SE) – 1 to 2 minutes after each injection to assure that the optic nerve is perfused.
- Ophthalmologic exam/Tonometry (SE) – At least 30 minutes after the second injection, a full ophthalmologic exam must be performed and IOP must be < 30 mmHg before the subject leaves the clinic.

3-Day Post-Injection Safety Check (± 1 day)

- Telephone call to subject to ensure there are no signs or symptoms of retinal detachment or endophthalmitis.

10.2.4 Day 9 Visit – Subjects in the DLT cohort only. The DLT cohort is defined as the first 3-6 subjects (depending on if DLTs are noted) enrolled in Cohort 1.

- Vital signs
- Protocol refraction and visual acuity (4 meters) using ETDRS chart (SE)
- Ophthalmologic examination and Goldmann applanation tonometry (SE)
- Spectral Domain optical coherence tomography (SD-OCT) (SE)
- Laboratory tests

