10.3.2 Day 1 Visit

Pre-injection

- Protocol refraction and visual acuity (4 meters) using ETDRS chart (SE)
- Goldmann applanation tonometry and ophthalmologic examination (SE)

Injection

- Lucentis® 0.5 mg/eye – administered 1st
 - Indirect Ophthalmoscopy (SE) – 1 to 2 minutes after the injection to assure that the optic nerve is perfused.
 - Ophthalmologic exam/Tonometry (SE) – After the injection, to confirm perfusion of the optic nerve and return of IOP to ≤ 21 mmHg or within 5 mmHg of pre-injection.
- Zimura™ 2 mg/eye – administered 2nd

Post 2nd Injection

- Indirect Ophthalmoscopy (SE) – 1 to 2 minutes after the injection to assure that the optic nerve is perfused.
- Ophthalmologic exam/Tonometry (SE) – At least 30 minutes after the second injection, a full ophthalmologic exam must be performed and IOP must be < 30 mmHg before the subject leaves the clinic.

3-Day Post-Injection Safety Check (± 1 day)

- Telephone call to subject to ensure there are no signs or symptoms of retinal detachment or endophthalmitis.

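### SAP 7.7 applies a 25-minute minimum to the IOP value after the first of two injections, so a compliant earlier reading is left out of the IOP tables and plot unless redacted Section 17.4 sets 25 minutes or later

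*SAP*

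**What the plan says.** SAP 7.7 (Intraocular Pressure) gives one definition for the value after the first and after the second injection: "the IOP measurement that is closest in time to the protocol-specified post-injection timepoint (but at least 25 minutes post-injection"). Its only other selection rule is a tie-break in favour of the later reading. Nothing in it refers to the time of the second injection. The same values feed the by-visit summary, the table of IOP categories and the figure: "Mean IOP over time of all scheduled measurements (pre-injection, IOP after first injection, and IOP after second injection) will be plotted".

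Protocol 7.2 describes the reading between two same-day injections by its purpose. Tonometry is repeated to confirm "return of IOP to ≤ 21 mmHg or within 5 mmHg of pre-injection before the second injection is administered". The visit text agrees, for example in 10.3.2: "After the injection, to confirm perfusion of the optic nerve and return of IOP to ≤ 21 mmHg or within 5 mmHg of pre-injection". Neither gives a number of minutes. A clock time appears only for the last or only injection of the day. On two-injection days it is "At least 30 minutes after the second injection, a full ophthalmologic exam must be performed" (10.2.3), and on single-injection days "At least 30 minutes after the injection a full ophthalmologic exam must be performed" (10.2.2). Footnote 4 of the schedule in protocol Section 3 also requires tonometry "at any additional times as specified by the Intravitreal Administration Protocol (see Section 17.4"). That section is redacted in the public copy.

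For baseline, SAP 7.7 averages the Screening and Day 1 pre-injection readings and adds: "Non-integer values for the average will be rounded up prior to subsequent calculations of change from baseline".

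**The concern.** The 25-minute floor suits a reading scheduled at 30 minutes or later. It does not obviously suit a reading whose timing depends on how quickly pressure recovers. If IOP meets the recovery condition before 25 minutes, the site may comply with the visible protocol and still produce a reading that the SAP rule rejects.

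The first-injection entry for that visit is then most naturally missing. SAP 3.3.3 and 7 do not impute and summarise observed cases, so n falls and the category percentages rest on a smaller denominator.

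Safety is the trial's only objective, IOP is a named safety endpoint, and no formal hypothesis testing is planned. The descriptive tables and plot are therefore the main output for this endpoint.

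**Working it through.** The plan states no figure on this point, so there is none to reproduce. The check applies the rule to the visible text and counts how often it could matter.

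**1. The rule applied.** Let t be the minutes from the first injection to the between-injection reading. SAP 7.7 admits the reading only if t ≥ 25. Readings at t = 5, 10, 15, 20 or 24 are rejected; readings at 25 or 30 are kept. On a single-injection day the protocol reading comes at 30 minutes or later, so the floor does no harm there. The same holds after the second injection of a two-injection day.

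**2. Exposure.** Cohort sizes and dosing come from protocol 6 and 11.1.

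| Cohort | n | Two-injection days per subject | Single-injection days per subject | Two-injection days | Single-injection days |
|---|---|---|---|---|---|
| 1 | 10 | 6 (D2) | 6 (D0) | 60 | 60 |
| 2 | 10 | 6 | 0 | 60 | 0 |
| 3 | 20 | 3 + 3 = 6 | 3 (D14) | 120 | 60 |
| 4 | 20 | 3 + 3 = 6 | 3 (D14) + 3 (D0) = 6 | 120 | 120 |
| All | 60 | | | 360 | 240 |

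Total injection days: 360 + 240 = 600, of which 360/600 = 60% have two injections. Total injections: 2 × 360 + 240 = 960. The first-injection values at risk are therefore 360/960 = 37.5% of planned after-injection values. This is exposure, not loss: the documents give no reading times.

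**3. Where those days fall.** From Day 1 to Month 2 the two-injection day is D0 in Cohorts 2, 3 and 4 and D2 in Cohort 1. At Months 3 to 5 it is D0 in Cohorts 2 and 3 and D2 in Cohorts 1 and 4. Every subject has one per monthly cycle.

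**4. Which between-injection reading.** If several are taken, the last is the one that met the condition in protocol 7.2, so its ceiling is max(21, pre-injection + 5) mmHg. For pre-injection IOP of 10, 15, 20 and 24 the ceiling is 21, 21, 25 and 29. The last compliant reading cannot reach 30 unless pre-injection IOP is at least 25. Choosing the last reading would therefore build the recovery condition into the summary.

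**5. Baseline rounding.** Assume whole-mmHg readings. The mean of two integers is then an integer or ends in .5, so rounding up adds 0 or 0.5. Example: readings of 15 and 16 give a mean of 15.5, rounded to 16. A later reading of 21 is a rise of 5.5 from the mean but is reported as 5. The shift never goes the other way.

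**The case against.** The strongest objection is that the gap may come from redaction. SAP 7.7 presupposes a protocol-specified timepoint, and the schedule footnote and protocol 9.2.4 both point to Appendix 17.4, which cannot be read. If 17.4 sets 25 minutes or later, compliant readings are selected correctly and only the ordering sentence is missing. This stands, and the conclusion is conditional on it.

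It is also fair that the practical consequence is limited. Rejected readings remain in the listings, which under SAP 3.3.1 include time of tonometry. IOP after the final injection is still tabulated, and increased intraocular pressure is counted among ocular TEAEs.

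Three stronger readings are tempting, and the documents do not support them.

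- A reader might infer that the reading after the second injection will fill both rows. It would pass the floor: with the second injection g minutes after the first, it falls at least g + 30 minutes after the first. But SAP 7.7 names the two values separately, and the schedule footnote distinguishes tonometry after the first from tonometry after the final injection. A missing entry is the natural outcome. The literal wording does not exclude double use, so an ordering sentence is still worth adding.
- A reader might infer that the loss falls on Cohorts 2 and 3 and distorts the cohort comparison. That holds only for the Month 3 to 5 D0 visits. Cohorts 1 and 4 face the same exposure at D2 two days later, and exposure per subject is equal in all four cohorts.
- A reader might infer a number or percentage of lost values. Nothing in the documents supports one.

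**Conclusion.** The concern holds in a conditional form. SAP 7.7 applies a 25-minute minimum to the first-injection value and does not require that value to precede the second injection. On the visible protocol, a compliant early reading on a two-injection day is left out of the IOP summary, category table and plot. This rests on one assumption: that Section 17.4 does not set the between-injection reading at 25 minutes or later. The missing ordering condition remains whatever 17.4 says.

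The size is 360 of 600 planned injection days exposed, six per subject, with an unknown number affected. The baseline rounding is a separate and minor matter: at most 0.5 mmHg, always towards a smaller rise, given whole-mmHg readings. Both are worth correcting because the endpoint is a safety endpoint and the corrections are nearly free. Neither threatens the trial.

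**What to change.** The change is to the analysis only; no clinical timing is proposed.

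- Reconcile SAP 7.7 with protocol 7.2 and Section 17.4. If 17.4 sets a time for the between-injection reading, name it in the SAP.
- On two-injection days, take the first-injection value only from readings before the second injection. Drop the 25-minute floor for that value unless 17.4 sets 25 minutes or later.
- Prespecify one selection rule, for example the first between-injection reading. The highest reading is a less clean choice because it tends to rise with the number of checks, and the last is bounded by the recovery condition.
- Report elapsed time and the number of subjects with a reading beside the row.
- Keep the floor for the last or only injection of the day.
- Calculate change from the unrounded baseline mean.

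The cost is SAP wording and minor programming, since tonometry times are already collected. The downside is that elapsed times will vary, so the first-injection row is not directly comparable with the second-injection row or with single-injection days. If a site records only the reading that met the recovery condition, the choice of rule makes no difference and the ceiling in step 4 still applies. The rounding change costs nothing.
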